3.2 Purpose of Study/Potential Impact

It has been purported that nipple stimulation may help induce labor and has been successfully utilized for inducing contractions for the purposes of contraction stress testing. It may be an attractive option for induction of labor for both de-medicalization of birth, patient satisfaction, cost reduction, and other clinical benefits. The purpose of this clinical trial is to determine whether nipple stimulation can increase the likelihood of a spontaneous vaginal delivery, and therefore decrease the likelihood of an operative vaginal or cesarean delivery. We also seek to examine whether intrapartum nipple stimulation can decrease labor duration and improve other patient-centered outcomes such as patient pain score, patient agency, patient satisfaction, depression scores, and breastfeeding success. Further, we aim to examine whether breast stimulation is associated with any significant differences in fetal or neonatal outcomes.

We propose a multicenter randomized trial at Yale, Weill Cornell Medicine and Northwestern Universities to compare inpatient nipple stimulation therapy via electric breast pump versus immediate synthetic oxytocin infusion without nipple stimulation for nulliparous women undergoing labor induction. This trial of 988 nulliparous women will provide adequate statistical significance to detect clinically meaningful differences in delivery mode and breastmilk as the sole source of nutrition for newborns. Successful completion of this proposal will provide rigorous data to help us show how this novel and potentially cost-effective method can radically change the way we induce labor and positively impact breastfeeding success and early infant nutrition through lactation.

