5.2.2 Secondary and Exploratory Outcome Variables (if applicable)

The following secondary maternal outcomes will be explored:

- Operative vaginal delivery (defined as delivery with the assistance of forceps or vacuum) and indication
- Cesarean delivery and indication
- Interval from randomization to delivery
- Postpartum hemorrhage (defined as a cumulative blood loss of $\geq 1,000$ mL within 24 hours after the birth process)
- Severe postpartum hemorrhage (defined as any of the following: transfusion; non-elective hysterectomy; use of ≥ 2 uterotonic medications other than oxytocin; other interventions such as uterine compression sutures, uterine artery ligation or embolization, hypogastric artery ligation, balloon tamponade)
- Suspected intraamniotic infection, intrapartum chorioamnionitis, or postpartum endometritis (defined as maternal fever $\geq 38^{\circ}$ Fahrenheit with planned or initiated administration of therapeutic antibiotics) after randomization and prior to delivery hospitalization discharge
- Third- or fourth- degree perineal lacerations
- Lactational mastitis (assessed up to 12 weeks postpartum from breastfeeding survey performed at 4-12 weeks postpartum and medical records)
- Maternal death (assessed until delivery hospitalization discharge)
- Admission to Intensive Care Unit (assessed until delivery hospitalization discharge)
- Subject-reported pain experienced during childbirth using the visual analog scale (28) , measured at 2 hours after start of intervention
- Subject-reported feelings of control during labor using the Labor Agency Scale (29) , assessed during the hospital postpartum stay
- Subject-reported satisfaction with the birthing experience using the validated Birth Satisfaction Scale-Revised (BSS-R) (30) (31), assessed during the hospital postpartum stay
- Subject-reported ability to express and/or collect colostrum and/or breastmilk intrapartum
- Subject-reported perception of milk supply using the validated Perception of Insufficient Milk Supply (PIMS) (40), 2 weeks postpartum

- Subject-reported depression score using the validated Edinburgh Postnatal Depression Scale, assessed (32), 4-12 weeks postpartum
- Subject-reported breastfeeding success using the validated Maternal Breastfeeding Evaluation Scale (MBES) (33), assessed 4-12 weeks postpartum
- Subject-reported breastfeeding success by assessing infant feeding method (breastmilk, formula, or combination) via questionnaire, assessed 6 months postpartum

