The primary outcome (spontaneous vaginal delivery) and other categorical secondary outcomes will be compared between trial groups using Chi-square or Fisher's exact tests as appropriate. The estimates of the relative risk and 95% confidence intervals (95% CI) associated with the primary and secondary outcomes will be calculated using Agresti and Coull method. The time to event regression analyses for labor length (regardless of delivery mode) and labor length censored for cesarean will be evaluated by Kaplan-Meier estimates and plots, and tested with the log-rank test, whereas Cox proportional hazards analysis will be used in adjusted analyses accounting for Bishop scores at study entry (proportionality assumption will be checked graphically with $\ln(-\ln\text{Survival})$ plots), and results summarized using hazard ratios (HR) and 95% CI). A sensitivity analysis will be performed using the induction method that the patient actually received (per-protocol analysis) to determine whether crossovers influenced the results. The distribution of maximal percent newborn weight loss is not expected to follow a normal distribution in the population, so we plan to use Wilcoxon Rank Sum Tests to compare the distribution of the maximal percent weight loss between treatment groups, and summarize the results as medians (25th and 75th percentiles) and bootstrapped 95% CIs. Similarly, the distributions of the PIMS survey scores and MBFES survey scores are not expected to follow normal distributions in the population, so we will use Wilcoxon Rank Sum Tests to compare the distribution of the MBFES scores between treatment groups and summarize the results using the group medians (25th and 75th percentiles) and bootstrapped 95% CIs.

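### Kaplan-Meier curves for labor length with cesarean censored overstate the probability of vaginal delivery over time; cesarean should be handled as a competing event

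*Protocol*

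**What the plan says.** Section 6.4.3.1 of the protocol plans two time-to-event analyses of labor length: "labor length (regardless of delivery mode) and labor length censored for cesarean will be evaluated by Kaplan-Meier estimates and plots". The first counts every delivery. The second treats cesarean as censoring. Both are then "tested with the log-rank test, whereas Cox proportional hazards analysis will be used in adjusted analyses accounting for Bishop scores at study entry". The only model assumption for which a check is named is proportional hazards. Independence of the censoring is not discussed, and no cumulative incidence function or other competing-risk method appears in the protocol.

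Three other places bear on whether cesarean can be treated as ordinary censoring:

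- Section 3.2 gives the trial's purpose as finding out whether nipple stimulation can "increase the likelihood of a spontaneous vaginal delivery, and therefore decrease the likelihood of an operative vaginal or cesarean delivery".
- Section 5.2.2 lists "Cesarean delivery and indication" as a secondary outcome in its own right.
- Section 6.3, on subject management, ties cesarean for failed induction to a lack of contractions and cervical change. It leaves nipple stimulation time out of the clock for that diagnosis.

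**The concern.** With cesarean censored, the only event left is vaginal delivery, spontaneous or operative. Kaplan-Meier treats a censored woman as still able to have the event later. A woman delivered by cesarean cannot. The proportion who ever deliver vaginally levels off at one minus the cesarean rate, whereas 1-KM keeps rising towards 100%. The overstatement is therefore built into the estimator whenever cesareans occur, and only its size depends on the data.

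A reader could try to rescue the curve as the labor length that would be seen if no cesareans were done. That reading needs cesarean to be independent of how labor would otherwise have progressed. The failed-induction criterion in section 6.3 makes this implausible.

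Shorter labor induction is part of the central hypothesis in section 4.1, so these curves are likely to be reported and read as the chance of vaginal delivery by a given hour. The trial expects the arms to differ in operative delivery, so the two curves would be inflated by different amounts.

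**Working it through.** **Inputs.** The protocol states no figure for the labor-length analysis, so there is none to reproduce. Section 6.4.2 assumes spontaneous vaginal delivery in 74% versus 64%. Operative vaginal and cesarean delivery together are then 26% and 36%, which are upper bounds for cesarean. Cesarean rates of 15% to 36% and the delivery times below are assumptions.

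**Formulas.** Let c be the cesarean share and S(t) the proportion still undelivered at time t. If both modes share one time distribution, the hazard of vaginal delivery is (1-c) times the total hazard, so:

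- 1-KM with cesarean censored = 1 - S(t)^(1-c)
- true cumulative incidence of vaginal delivery = (1-c) × (1 - S(t))

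**Constant hazards, median 18 h to any delivery.** S(t) = exp(-t × ln 2 / 18), so S(24) = 0.397 and S(48) = 0.158.

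| c | time | 1-KM | cumulative incidence | excess (points) |
|---|---|---|---|---|
| 15% | 24 h | 54.4% | 51.3% | 3.1 |
| 15% | 48 h | 79.2% | 71.6% | 7.6 |
| 26% | 24 h | 49.5% | 44.6% | 4.9 |
| 26% | 48 h | 74.5% | 62.3% | 12.2 |
| 36% | 24 h | 44.6% | 38.6% | 6.0 |
| 36% | 48 h | 69.4% | 53.9% | 15.5 |

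**Gamma times, shape 3, mean 18 h for both modes (simulation of 400,000).**

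| c | time | 1-KM | cumulative incidence | excess (points) |
|---|---|---|---|---|
| 15% | 24 h | 70.4% | 64.7% | 5.7 |
| 15% | 48 h | 97.4% | 83.8% | 13.6 |
| 26% | 24 h | 65.4% | 56.3% | 9.1 |
| 26% | 48 h | 95.8% | 72.9% | 22.9 |
| 36% | 24 h | 60.1% | 48.8% | 11.3 |
| 36% | 48 h | 93.5% | 63.2% | 30.3 |

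The formulas agree with the simulation. For c = 26% at 24 h, S(24) = exp(-4) × (1 + 4 + 8) = 0.238, so 1-KM = 1 - 0.238^0.74 = 0.654 and the true value is 0.74 × 0.762 = 0.564. If cesareans come later (mean 24 h), the excess at 26% is smaller: 5.8 points at 24 h and 17.9 at 48 h. Over all these settings the excess is about 3 to 11 points at 24 h and 8 to 30 points at 48 h.

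**Effect on the comparison of arms.** Suppose the intervention lowers cesarean by 10 points and leaves delivery times within each mode unchanged (gamma times, 48 h):

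| cesarean, control to intervention | mean cesarean time | true difference (points) | Kaplan-Meier difference (points) |
|---|---|---|---|
| 36% to 26% | 18 h | 10.0 | 2.3 |
| 36% to 26% | 24 h | 9.9 | 5.6 |
| 25% to 15% | 18 h | 10.0 | 1.5 |
| 25% to 15% | 24 h | 10.1 | 4.1 |

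A true difference of about 10 points appears as 1.5 to 5.6 points, in the same direction.

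**The case against.** The best defense is that the inference in this section is sound. A log-rank test or Cox model with cesarean censored is a standard comparison of the cause-specific hazard of vaginal delivery, and needs no independent-censoring assumption to be read that way. This stands. The fault lies in the Kaplan-Meier estimates and plots.

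Next, the listed time outcome is "Interval from randomization to delivery", meaning any delivery. The analysis regardless of delivery mode matches it and has no competing event. This also stands: the listed outcome is not affected, and the cesarean-censored analysis is a second view of labor length.

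Third, the protocol never says that the censored curve will be read as the proportion delivered vaginally, and it names no median labor time as a summary. Delivery-mode proportions are compared separately, by chi-square or Fisher tests. This lowers the stakes, but a Kaplan-Meier plot of this kind invites that reading, and the plan sets no other.

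Fourth, the figures rest on assumed rates and times and show the gap between two estimands. They do not measure how strongly cesarean depends on slow labor. That is fair, and is why a range is given.

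A reader might go further and infer that an arm with more cesareans will look faster under this analysis. The calculations do not support that. With constant hazards and a mean of 20 h, an arm with 28% cesarean has 1-KM of 57.9% at 24 h and 82.2% at 48 h, against 61.7% and 85.3% for an arm with 20%. The arm with more cesareans looks slower. The true values are 50.3% and 65.5% against 55.9% and 72.7%, so true gaps of 5.6 and 7.3 points shrink to 3.8 and 3.1 (from the rounded figures). The gap is attenuated and keeps its direction.

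**Conclusion.** The point holds for the cesarean-censored Kaplan-Meier estimates and plots. They overstate the cumulative probability of vaginal delivery in both arms, more in the arm with more cesareans, and tend to hide part of a true benefit if the intervention works by lowering cesarean. That an overstatement exists follows from cesarean precluding vaginal delivery. Its size is conditional on the assumed cesarean rates and delivery times, which the protocol does not give.

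This is a worthwhile correction to one of two analyses of a secondary question. It does not touch the primary chi-square comparison or the 988 participants. A statistical analysis plan that is not shown could add a competing-risk method, but the protocol as written fixes Kaplan-Meier.

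**What to change.** In section 6.4.3.1:

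- Replace the cesarean-censored Kaplan-Meier estimates and plots with Aalen-Johansen cumulative incidence of vaginal delivery from randomization, with cesarean as the competing event. Show the cumulative incidence of cesarean beside it.
- Compare the arms by Gray's test or a Fine-Gray model, which can carry the Bishop score as a covariate.
- Keep the cesarean-censored log-rank test and Cox model, labeled as comparisons of the cause-specific hazard of vaginal delivery.
- Keep the analysis regardless of delivery mode as it is.

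The cost is a change of wording. The data are already collected and the methods are standard. The downside is one more estimate to explain.

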This is a multi-site, pragmatic, open label parallel group randomized clinical trial of pregnant women at 36 weeks of gestation and greater to compare the effectiveness of inpatient nipple stimulation therapy with or without adjunctive synthetic oxytocin (intervention) versus immediate synthetic oxytocin infusion without nipple stimulation (comparator) during labor induction at Yale New Haven Hospital, Weill Cornell Medicine and Northwestern Memorial Hospital.

Study Population

Nulliparous women with live singleton gestations of 36 weeks and greater and are planned to receive synthetic oxytocin infusion for induction of labor.
Number of Participants A total of 988 participants will be enrolled across all study sites with roughly even distribution.
Number of Study Sites The trial will be conducted at 3 sites: Yale New Haven Hospital (York Street Campus), Weill Cornell Medicine and Northwestern Memorial Hospital.
Primary Outcome Variables The primary outcome is spontaneous vaginal delivery.

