6.1.3 Concomitant therapy

There are no restrictions on use of concomitant medications. However, for those who are randomized to nipple stimulation, the use of exogenous oxytocin intravenous solution will not be permitted until at least two hours of nipple stimulation alone has been attempted, unless this is decided by the treating obstetric provider. Stimulation may be discontinued at any time that the treating obstetric provider decides. If there are any signs of fetal heart rate abnormalities on the cardiotocography, the obstetric provider should provide usual care measures such as discontinuation of stimulation, lateral positioning, intravenous hydration, etc. Initiation of exogenous oxytocin intravenous solution prior to two hours of nipple stimulation alone will be considered a cross-over.

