6.4.2 Sample Size Considerations

1) Total sample size for the trial: The sample size for the trial is based on the primary outcome of spontaneous vaginal delivery. Therefore, the sample size of n=988 is selected for this proposed study to detect a 10% absolute increase while accounting for an expected 5% attrition rate. We then estimate, on the basis of the sample size for the primary outcome, the power we will have to detect clinically significant differences in the secondary outcomes.

Sample size estimation for primary outcome:

Detectable absolute difference	Anticipated with nipple stimulation therapy	Total Sample size Across 2 Study Groups for 90% power
15%	79%	426
14%	78%	492
13%	77%	574
12%	76%	676
11%	75%	812
10%	74%	988
9%	73%	1,222

All sample size and power estimates are based on two-tailed tests. *This is important because we will be powered to detect both increases and decreases in outcomes with intrapartum nipple stimulation therapy (intervention) versus immediate synthetic oxytocin infusion without nipple stimulation (comparator).* The expected rate of spontaneous vaginal delivery in the setting of immediate synthetic oxytocin infusion without nipple stimulation used for the sample size estimation is based on averaged institutional data from the study sites. We estimate that a total of **988** (494 nipple stimulation therapy and 494 immediate synthetic oxytocin infusion without nipple stimulation) will be sufficient to detect a **10% absolute difference** (estimated 74% versus 64%) in spontaneous vaginal delivery with 90% power (alpha of 0.05).

Justification: At first glance, the anticipated 10% or greater absolute increase in the spontaneous vaginal delivery rate in our proposed trial appears modest. On the contrary, because the potential public health impact is large, this effect size is significant. It is estimated that 40% of the *one million* women who undergo inpatient labor induction each year in the U.S. are nulliparas. Therefore, a 10% increase in spontaneous vaginal delivery translates to 40,000 more spontaneous vaginal deliveries and *40,000 fewer operative deliveries each year*. Avoiding 40,000 operative deliveries each year will have substantial impact on overall morbidity and healthcare resource utilization in the U.S. and beyond.

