6.4.3 Planned Analyses

6.4.3.1 Primary Analyses

1) Overview: Data analyses will adhere closely to the CONSORT guidelines. Analyses will follow the intention-to-treat principle in which subjects will be analyzed in the group to which they were randomized, regardless of whether or not they received the assigned intervention.

2) Primary Analyses:

Descriptive statistics will characterize the group of individuals recruited and investigate comparability of the two study groups at baseline. Formal statistical testing will be limited to select baseline characteristics considered to be prognostic factors for the primary outcome including hospital admission body mass index (BMI), primary indication for labor induction, Bishop score at randomization, and birth weight. Categorical variables will be compared between trial groups by using the Chi-squared or Fisher's exact tests as appropriate, and continuous variables will be compared using Student's t-test or Wilcoxon Rank Sum Test, as appropriate. Distributions of continuous variables will be assessed by visual inspection of histograms.

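### The planned cross-over sensitivity analysis is an as-treated comparison labelled per-protocol, and it cannot separate selection from a cross-over effect

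*Protocol*

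**What the plan says.** The primary analysis is by intention to treat: "subjects will be analyzed in the group to which they were randomized, regardless of whether or not they received the assigned intervention" (Protocol 6.4.3.1; 5.1 and 6.4.1 say the same). Section 6.4.3.1 then adds a sensitivity analysis "using the induction method that the patient actually received (per-protocol analysis) to determine whether crossovers influenced the results".

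Three other places bear on how that sentence can be read:

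- Section 6.1.3 defines the event: "Initiation of exogenous oxytocin intravenous solution prior to two hours of nipple stimulation alone will be considered a cross-over". The treating provider may decide on oxytocin before two hours.
- The Synopsis (Study Design) describes the assigned strategy as "inpatient nipple stimulation therapy with or without adjunctive synthetic oxytocin (intervention"), and section 5.1 agrees. Oxytocin added after two hours is thus part of the intervention.
- Section 6.3 (Subject Management and Follow-Up) leaves any change to oxytocin to the provider's individual judgement of how labour is advancing and how the fetus is responding, with no fixed time limit. Section 6.1.2 says blinding is not possible.

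**The concern.** The label and the rule describe different analyses. A per-protocol set keeps each woman in the arm to which she was randomised and drops those who did not adhere. Grouping by method received moves women from one arm to the other.

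The move depends on a decision taken during labour, without blinding, on signs that also bear on mode of delivery. Women moved out of the stimulation group would be expected to have slower or more difficult labours than those who stay. Their removal raises the stimulation rate and their arrival lowers the oxytocin rate. Controls who progress without oxytocin, as one of six did in the pilot (section 2.1), could leave the oxytocin group and push the same way.

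This is the only analysis specified to show whether cross-overs mattered. If it differs from intention to treat, the reader cannot tell selection from a true effect of crossing over. In an open-label trial, a larger result labelled per-protocol could be taken as support for the main finding.

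**Working it through.** **Design figure first.** Section 6.4.2 sets 988 women for 74% against 64% "in spontaneous vaginal delivery with 90% power (alpha of 0.05"), two-tailed, "to detect a 10% absolute increase while accounting for an expected 5% attrition rate". The continuity-corrected two-proportion formula gives 468 per arm, or 936; 936/0.95 = 985.3, so 986 with equal arms, against 988 stated. The design effect of 10 points is therefore a sound yardstick.

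**Inputs.** Allocation is 1:1 (6.1.2). Assume no true effect, with p = 64% in both randomised arms. Let f be the share of the stimulation arm moved to the oxytocin group, and g the amount by which spontaneous vaginal delivery is lower in those moved than in those who stay. The protocol gives neither f nor g for this trial. Its only figure is the pilot (2.1): 1 of 18 stimulation-arm women crossed over. The protocol quotes this as 1/24 (4.2%); within the arm it is 1/18 = 5.6%.

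**Formula.**

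- Those who stay: s = p + fg. Those moved: m = s − g.
- As-treated oxytocin group: (p + fm)/(1 + f).
- False difference: s − (p + fm)/(1 + f) = 2fg/(1 + f).

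**Results under no true effect** (differences from unrounded rates):

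| f | Rate in those moved | g (points) | Stimulation group | Oxytocin group | False difference (points) |
|---|---|---|---|---|---|
| 1/18 | 50% | 14.8 | 64.8% | 63.3% | 1.6 |
| 1/18 | 40% | 25.4 | 65.4% | 62.7% | 2.7 |
| 1/18 | 20% | 46.6 | 66.6% | 61.7% | 4.9 |
| 1/18 | 0% | 67.8 | 67.8% | 60.6% | 7.1 (ceiling) |
| 15% | 38.5% | 30 | 68.5% | 60.7% | 7.8 |
| 20% | 40% | 30 | 70.0% | 60.0% | 10.0 |
| 30% | 50% | 20 | 70.0% | 60.8% | 9.2 |
| 50% | 54% | 20 | 74.0% | 60.7% | 13.3 |

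**Gap needed for 10 points:** g = 0.10(1 + f)/(2f). This is 95 points at f = 1/18 (not attainable, since g cannot exceed 67.8 there), 55 at 10%, 30 at 20% and 22 at 30%.

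**Precision of the pilot rate.** The upper exact 95% limit for 1/18 solves (1 − p)^18 + 18p(1 − p)^17 = 0.025, giving p = 0.273. A 20% rate is thus not excluded, but neither is it documented.

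**If cross-overs are only excluded** from the stimulation arm, the bias is fg: 6.0 points at f = 20% and g = 30, and 0.8 to 2.6 points at f = 1/18 with 50% to 20% delivering spontaneously. It is smaller but not zero.

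**If controls without oxytocin are dropped as well,** at the pilot's 1/6 and with an assumed 80% to 100% of them delivering spontaneously, the as-treated difference at f = 1/18 is 4.7 points (those moved 50%, controls 80%) to 12.1 points (20% and 100%). These prognoses are assumptions, and one of six is a very weak basis.

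**The case against.** The strongest reply is that the analysis exists to examine cross-overs, and section 6.1.3 says what those are. On that reading few women move, and at the pilot rate the bias stays well below the design effect. This stands, and it limits the size of the problem.

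A reader might infer that the analysis would produce a false benefit as large as the design effect. The protocol does not support that. It requires cross-over rates and outcome gaps that the document does not give, or it requires counting oxytocin after two hours as oxytocin received, contrary to the Synopsis and sections 5.1 and 6.1.3. The sensitivity sentence does not rule out that second reading, because a woman who had both methods received both, but nothing directs it.

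A reader might also infer that the bias must always favour stimulation. That is too strong. The one pilot cross-over withdrew over delayed care, which is not described as slow labour.

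Detailed rules for analysis sets may properly sit in a statistical analysis plan that is not shown. But the protocol sentence already fixes a grouping rule and a label, and the two disagree. No sample size, alpha or decision rule rests on this analysis.

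**Conclusion.** The point holds for a supportive analysis only. The analysis as worded is as-treated, mislabelled per-protocol, and regroups women on a post-randomisation clinical decision, so it cannot answer its own question.

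At the pilot stimulation-arm rate the expected false benefit is about 2 to 5 points, assuming 50% down to 20% spontaneous delivery in those moved, with a ceiling of 7.1 from that source alone. Ten points needs, for example, 20% moved with a 30-point gap. Confidence is high on the label and mechanism and low on the magnitude, because f and g are assumed. The intention-to-treat result is not affected.

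**What to change.** Replace the sentence with an analysis that keeps women in their randomised arms and takes non-adherence from section 6.1.3: oxytocin before two hours of stimulation alone is a cross-over, and later oxytocin remains adherent. State how controls who never receive oxytocin are classed. Then use one of these:

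- **Preferred:** a complier-average effect with randomised arm as instrument. Under no true effect and a valid exclusion restriction it is centred on zero. With cross-over in the stimulation arm only, it is the intention-to-treat difference divided by (1 − f).
- **Alternative:** a per-protocol set so defined, adjusted for baseline prognostic factors and labelled as a non-randomised comparison.

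The cost is one sentence and a small extra analysis, with no change to clinical management. The complier interval is wider, by about 1/(1 − f): 1.06 times at f = 1/18 and 1.25 times at 20%. It also relies on an exclusion restriction that partial stimulation before crossing over may strain. The per-protocol set keeps some selection bias. These limits should be stated beside the result.
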